3. DESCRIPTION OF DESIGN AND TRIAL POPULATION

3.1 OVERALL TRIAL DESIGN AND PLAN

This is a Phase I/II open-label, dose escalation study to determine the MTD of afatinib as single agent and to assess its anti-tumour activity in children with recurrent or refractory malignant neuroectodermal tumours, RMS and/or other solid tumours with ErbB pathway deregulations.

This phase I/II trial is connected to a translational biomarker prevalence study which is informative for the identification of possible biomarkers which are considered suitable for inclusion of patients in the MTD expansion cohorts/Phase II part. The biomarker prevalence study was conducted outside of this clinical trial. For details refer to [Section 2.1](#) and [Section 5.6](#). Results of the biomarker prevalence study are partially reported ([c09990672-01](#)).

This clinical trial has 2 parts (see [Figure 3.1:1](#)):

1. A dose finding part
2. A biomarker specific MTD expansion cohorts/Phase II part

The trial will end when the last patient has completed the 28-30 day safety follow-up (FU) visit. For additional information on trial termination, see also [Section 3.3.4.2](#) and [Section 8.6](#).

[figure not shown]

Figure 3.1:1 Trial design

1. **Dose finding part:** Accounting for the low incidence of each paediatric tumour entity within the above group and the heterogeneity of ErbB pathway deregulations described, the dose finding part of the trial will be conducted in paediatric patients with recurrent/refractory neuroectodermal tumours, and RMS, for whom no further treatment option exist and who are likely to derive benefit from treatment as their tumours are known to show ErbB deregulation in literature. In addition, patients with other solid tumours (regardless of histology) with known ErbB deregulations,

Proprietary confidential information.

© 2017 Boehringer Ingelheim International GmbH or one or more of its affiliated companies. All rights reserved.

This document may not - in full or in part - be passed on, reproduced, published or otherwise used without prior written permission.

assessed by institutional standards, may be included into this part of the trial. All of these patients will be included to determine the MTD. A rolling-6 design will be used for patients' assignment to dose cohorts (see [Table 4.1.4.1:1](#)).

Patients in Phase I dose finding part will undergo retrospective testing for ErbB deregulation.

This part was completed ([c09990672-01](#)).

- 2. MTD expansion cohorts/Phase II part:** Once the MTD is determined, patients will be tested and recruited only if they fulfil at least two of the following biomarker criteria (i) EGFR gene amplification (FISH) *and/or* (ii) HER2 gene amplification (DDISH) *and/or* (iii) EGFR protein expression (membrane staining): H-score > 150 *and/or* (iv) HER2 protein expression (membrane staining): H-score > 0 ([see section 5.6](#)). A minimum of 5 patients in each of the four following cohorts, i.e. HGG, DIPG, EM and a mixed histology agnostic cohort of patients with refractory tumours, will be accrued to confirm a safe recommended Phase II dose (RPIID) and to be assessed for response. An exploratory cohort of a maximum of 6 patients with proven genomic, transcriptomic or proteomic ErbB alterations which are not defined above will also be included. This part of the trial will allow the collection of further safety and PK data to limit failure due to dosing issues in further clinical development, but also give insight if the "targeted" patient selection increases the level of clinical efficacy.

3.1.1 Administrative structure of the trial

The coordinating investigator is an expert in paediatric oncology with experience in new drug development. The coordinating investigator has been designated by Boehringer-Ingelheim and will sign the clinical trial report. Selected investigators from the network of "Innovative Treatments for Children with Cancer (ITCC)" and other participating investigators are likewise experts in the paediatric oncology with experience in this type of trial and investigations and in new drug development.

A steering committee including the coordinating investigator, selected ITCC investigators in different EU countries, non-ITCC in non-EU countries and BI representatives, will monitor the study on a regular basis (recruitment issues, data quality, decisions on dose escalation, etc.).

A data monitoring committee (DMC) will be appointed by BI. The DMC will consist of an independent, multidisciplinary group who have expertise in paediatric oncology and new drug development trials in children. A statistician must be part of this group. The DMC's responsibility will be the continuous assessment of the trial data to ensure the overall benefit/risk of the patients treated and to monitor the quality of the trial. The DMC will advise BI and the steering committee about the conduct of the trial and the integrity of the data. Regular safety review and benefit/risk assessment will be performed by the DMC as described in the DMC charter. The latter defines but is not limited to e.g. a regular DMC meeting schedule, adhoc meetings in case of unexpected SAE, regular AE listings to be provided by the sponsor, etc.. The DMC will guide the sponsor throughout the trial.

Proprietary confidential information.

© 2017 Boehringer Ingelheim International GmbH or one or more of its affiliated companies. All rights reserved.

This document may not - in full or in part - be passed on, reproduced, published or otherwise used without prior written permission.

3.2 DISCUSSION OF TRIAL DESIGN, INCLUDING THE CHOICE OF CONTROL GROUP(S)

Since the implementation of the Regulation (EC) No 1901/2006 of the European Parliament ([R09-2583](#)) numerous paediatric development programs on new oncology compounds started but Paediatric Investigation Plans (PIPs) were driven by adult indications, which were not waived for children, rather than by a paediatric unmet medical need ([R13-1146](#)). Where pursued, paediatric development is frequently hampered by an early focus on rare indications with lack of feasibility of patient recruitment. In contrast, trials set up too broadly provided scattered evidence of clinical activity but were neither evaluable for effect size per indication examined, nor for a biomarker enriched population, as biomarkers were frequently introduced retrospectively to help explaining an observed effect. Different compounds targeting similar pathways in relatively few paediatric cancer patients compete for patient accrual into clinical trials. If no clear working hypothesis/rationale for the assessment of a certain compound in a particular population is generated, it is difficult to convince cooperative groups and patients' guardians to recruit into these trials. BI proposes to conduct a Phase I trial in patients with relapsed and or poor prognostic neuroectodermal tumours, which are embryologically and ontogenetically derived from the same germinal sheet, and for which therefore some rationale for ErbB deregulation in tumour genesis can be hypothesized and evidence in the literature exists. In addition, the dose finding part of this trial allowed to include patients with solid tumours (regardless of histology) with known ErbB pathway deregulations, assessed by institutional standards— this part is completed ([c09990672-01](#)). The above described paediatric patients don't have further treatment options outside of clinical trials, but are likely to derive benefit from treatment with the ErbB family blocker afatinib as their tumours are known (i) to show ErbB deregulation per literature review , or (ii) demonstrated ErbB deregulation by institutional standards. Patients in the MTD expansion cohorts/Phase II part will be recruited based on ErbB pathway deregulations, defined in the biomarker prevalence study ([c09990672-01](#)), see also [Section 5.6](#). With the proposed design, three questions can be addressed at the same time: (i) identifying the right dose during the dose finding, (ii) hitting the right target, and (iii) the impact of targeted patient selection on efficacy. The basket approach will address feasibility of patient recruitment and the biomarker driven patient selection will address unanswered questions on ErbB deregulation. For patients' benefit refer to [Section 2.3](#).

Dose finding Part: A rolling 6 design will be used to determine the MTD. The MTD will be assessed by DLT as described in [Table 4.1.4.1:2](#). The MTD will be determined as the highest dose at which no more than 1/6 patients experienced DLT. The rolling 6 design was chosen to limit the waiting period for paediatric patients seeking treatment, as depicted below.

MTD expansion cohorts/Phase II part will recruit a minimum of 5 patients in each of the four disease specific cohorts for HGG, DIPG, EM and other solid tumours fulfilling ErbB biomarker selection criteria (see [Section 3.3.2](#)) and an exploratory cohort of patients with proven genomic, transcriptomic or proteomic ErbB alterations. Efficacy will be assessed by objective response (OR) and the OR rate must be considered meaningful by experts in the field of paediatric oncology and regulatory agencies to pursue further clinical development.

Proprietary confidential information.

© 2017 Boehringer Ingelheim International GmbH or one or more of its affiliated companies. All rights reserved.

This document may not - in full or in part - be passed on, reproduced, published or otherwise used without prior written permission.

Tumour material from all patients entered into this clinical trial must be available for retrospective testing of an ErbB pathway deregulation (for DIPG in dose finding part, see [section 3.3.2](#)) or prospective patient screening into the MTD expansion cohorts/Phase II part.

Intra-patient dose escalation: No clear exposure-efficacy correlation for afatinib has been identified in adult cancer patients yet. Conventional dosing in oncology trials is based on the MTD, or a recommended Phase II dose close to the MTD, dependent on overall safety. Treatment at lower dose tiers may be hampered by a presumed lack of efficacy. Assessment of the MTD or the recommended Phase II dose in oncology trials is based on a frequency of patients with DLTs. Trial 1200.120 will allow intra-patient dose escalation. As soon as the next higher dose tier is considered safe by standard DLT incidences in course one, patients of the lower dose tier, who benefit from treatment may resume treatment at the next higher dose. Although these patients will not be counted into MTD dose cohorts – see rolling 6 design- the safety database at the MTD level/ higher dose tiers and hopefully patients' benefit from participation in Phase I dose finding will be increased.

This part has been completed ([c09990672-01](#)).

3.3 SELECTION OF TRIAL POPULATION

17 patients were treated in the dose finding part to determine the MTD according to a rolling 6 design Skolnik et al ([R12-4744](#)). Once the MTD was determined, MTD expansion cohorts/Phase II part will include up to 38 additional patients who must be evaluable for OR. It is expected that up to 550 patients will need to be screened to treat 55 patients who will be evaluable for MTD/OR in the trial.

About 30 trial sites in EU/US/Canada are expected to recruit in this trial. The sites will have experience in paediatric oncology and in new drug development. All sites are willing to deliver tissue samples from recruited patients.

A log of all patients included into the study will be maintained in the ISF at the investigational site irrespective of whether they commenced trial drug or not.

The MTD expansion cohorts/Phase II part will provide biomarker specific efficacy data to establish proof of concept of anti-tumour activity of afatinib in ErbB deregulated paediatric cancer patients.

3.3.1 Main diagnosis for study entry

The proposed Phase I/II trial will include paediatric patients with refractory or recurrent HGG, DIPG, lower grade astrocytoma, neuroblastoma, ependymoma, medulloblastoma and PNET, rhabdomyosarcoma ([R13-0506](#), [R12-3164](#)), and/or other solid tumours with known ErbB pathway deregulation regardless of tumour histology.

3.3.2 Inclusion criteria

Phase I dose finding part

1. Patients with a histological diagnosis of high grade glioma (HGG), diffuse intrinsic pontine glioma (DIPG), low grade astrocytoma, medulloblastoma/PNET, ependymoma (EM), neuroblastoma, rhabdomyosarcoma and/or patients with other solid tumours (regardless of histology) but with known ErbB pathway deregulation
2. Patients must have recurrent or refractory disease following at least one prior standard treatment regimen
3. Patients aged between ≥ 2 to < 18 years*
4. Patients must have recovered (to CTCAE grade 1 or baseline) from any acute toxicity resulting from any prior anti-cancer treatment (except alopecia)
5. No effective conventional therapy exists
6. Patient assent and parent(s)/legal guardian(s)' written informed consent that is consistent with local law and ICH-GCP guidelines
7. Archival and/or fresh tumour tissue available. For DIPG, if the latter is not available, biopsy data on tumour histology and tumour profiling (if applicable) must be made available
8. Performance status: Lansky $\geq 50\%$ for patients ≤ 12 years of age or Karnofsky $\geq 50\%$ for patients older than 12 years of age assessed within two weeks prior to enrolment
9. Patients with CNS malignancies must be neurologically stable for at least 7 days before inclusion into the trial as per investigator judgement
10. Patients, both males and females, with reproductive potential (girls post menarche and males after 1st ejaculation) and sexually active must agree to practice highly effective contraceptive measures for the duration of study drug therapy and for at least 28 days after completion of study drug therapy (see [Section 4.2.3.3](#) for highly effective contraceptive measures)
11. Patients must be able and willing to swallow/take afatinib orally once daily (tablets or oral solution) as per investigator judgement
12. LVEF $\geq 50\%$

* In special cases where a patient / guardian(s) signed a pre-screening consent when the patient was 17 years old and the patient turns 18years before the trial consent was signed, the patient can be included in the trial.
In any case, the rate of patients >18 years at treatment start must not exceed 19% of the whole trial population

Inclusion criteria for MTD expansion cohorts/ Phase II part:

- Inclusion Criterion 1: Patients with HGG, DIPG, EM and other solid tumours than aforementioned which fulfil at least two of the below criteria:

Proprietary confidential information.

© 2017 Boehringer Ingelheim International GmbH or one or more of its affiliated companies. All rights reserved.

This document may not - in full or in part - be passed on, reproduced, published or otherwise used without prior written permission.

- EGFR gene amplification (FISH): Either $EGFR/Cen7 \geq 2.0$ or $\geq 10\%$ of cells with ≥ 15 copies or $\geq 40\%$ of cells with ≥ 4 copies or gene cluster in $\geq 10\%$ of cells *and/or*
- HER2 gene amplification (DDISH): $Her2/CEP17 \geq 2.0$ *and/or*
- EGFR protein expression: H-score > 150 (membrane staining) *and/or*
- HER2 protein expression: H-score > 0 (membrane staining)

Inclusion will be based on biomarker assessment prior to inclusion, as detected by central laboratory analysis of tumour biopsy material

- Inclusion criterion #3: Patients aged between ≥ 1 to < 18 years
- Inclusion criterion #7: Archival and/or fresh tumour tissue available.

Inclusion criteria 2, 4, 5, 6, 8-12 apply as above

- Inclusion criterion #13: Patients with proven genomic, transcriptomic or proteomic ErbB alterations which are not defined in the above inclusion criterion #1 regardless of tumour histology (See [Section 5.6](#), [tables 5.6:1 to 5.6:4](#)).
- Inclusion criterion #14: Patients must have at least one measurable lesion according to the institutional response criteria for the given tumour type.

3.3.3 Exclusion criteria

1. Chemotherapy within 3 weeks prior to the start of study treatment, biological therapy or investigational agents within 4 weeks prior to the start of study treatment or prior to passing 5 half-lives, i.e. systemic clearance, whatever comes first
2. Radiotherapy within 2 weeks before starting study treatment (palliative radiotherapy is allowed if not focused on a target lesion)
3. Surgery within 4 weeks before starting study treatment or planned surgery during the projected course of the study which compromises patient's trial participation by investigator judgement
4. Known hypersensitivity to afatinib or its excipients
5. History or presence of clinically relevant cardiovascular abnormalities as per investigator judgement
6. Female patients of childbearing potential, who are nursing or are pregnant
7. Any history of or concomitant condition that, in the opinion of the investigator, would compromise the patient's ability to comply with the study or interfere with the evaluation of the efficacy and safety of the test drug

Proprietary confidential information.

© 2017 Boehringer Ingelheim International GmbH or one or more of its affiliated companies. All rights reserved.

This document may not - in full or in part - be passed on, reproduced, published or otherwise used without prior written permission.

8. Requirement of treatment with a prohibited concomitant medication listed in the CTP that cannot be stopped for the duration of trial participation
9. Known pre-existing interstitial lung disease (ILD), or signs and symptoms indicative of the latter as per investigator judgement (see [Section 4.2.1](#))
10. Any history or presence of poorly controlled gastrointestinal disorders that could affect the intake/absorption of the study drug (e.g. Crohn's disease, ulcerative colitis, chronic diarrhoea, malabsorption) as per investigator judgement
11. Active hepatitis B infection (defined as presence of HepB sAg and/ or Hep B DNA), active hepatitis C infection (defined as presence of Hep C RNA) and/or known HIV carrier
12. Known keratitis
13. Inadequate liver function (AST/ALT>2.5xULN, Bilirubin>1.5xULN adjusted for age)
14. Inadequate kidney function, i.e. creatinine>1.5xULN adjusted for age and/or creatinine clearance <70 ml/min/1.73m² estimated by institutional standard formula for estimation of GFR in paediatric patients
15. Inadequate bone marrow function (ANC ≤1000/mm³, platelets ≤100000/mm³)

3.3.4 Removal of patients from therapy or assessments

3.3.4.1 Removal of individual patients

The Investigator, patient and/or parent/legal guardian may stop study treatment at any time for safety or personal reasons.

If a patient is entered in violation of inclusion/exclusion criteria, the sponsor, in discussion with the investigator and if needed DMC, will determine the medical benefit/risk on a patient-by-patient basis and can require such a patient be discontinued from the study treatment.

A patient is to discontinue study medication if:

- 1 The patient and/or parent/legal guardian withdraw assent/consent to continue therapy without the need to justify.
- 2 The patient is no longer receiving benefit from treatment, in the opinion of the investigator.
- 3 In the investigator's medical judgment, further participation would not be in the best interest of the patient, or might be injurious to the health and well-being of the patient
- 4 The patient is no longer able to participate for other medical reasons (e.g. surgery, adverse events, secondary malignancy, or other diseases)

Proprietary confidential information.

© 2017 Boehringer Ingelheim International GmbH or one or more of its affiliated companies. All rights reserved.

This document may not - in full or in part - be passed on, reproduced, published or otherwise used without prior written permission.

- 5 A female post-menarchal patient becomes pregnant ([Section 5.2.2.3](#))
- 6 The patient is diagnosed with ILD, keratitis or heart failure (including clinically relevant LVEF reduction) ([Section 4.2.1](#))
- 7 The patient needs further dose reductions considered necessary but not allowed according to the protocol ([Section 4.1.4.3](#))

The sponsor may remove patients from the study after completion of the primary analysis and grant access to afatinib via an alternative source e.g. through an expanded-access program, named patient use program, or compassionate use protocol.

Patient discontinuation of study participation:

A patient, who has discontinued study medication, will complete a follow-up (FU) visit 28-30 days after the last intake of the trial drug. After this FU visit, no further study procedure will be performed and the patient will enter the observation period during which only data collection on (S)AE(s) considered relevant by investigator, vital status and further anti-cancer treatment will be requested.

For all patients, the reason for withdrawal (e.g. adverse events) must be recorded in the eCRF. These data will be included in the trial database and reported.

If the patient and/or parents and/or legal guardian withdraw assent/consent to continue further trial procedures and the follow-up visit activities, no additional study assessments will be completed. In this event patients and parents or legal guardians will be asked whether they agree to allow continued further data collection of associated clinical outcome parameters during the observation period. If the patient/parents do not permit further contact/data collection this will be documented in the eCRF and in the source data.

Patients who withdraw from the trial after entering active treatment phase may be replaced if the primary endpoint of the respective trial phase is not achieved (see [Section 5](#)).

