4.1.4.3 Dose reduction of afatinib

Treatment related toxicities will be managed by treatment interruptions and subsequent dose reductions of afatinib according to the schedule described in [Table 4.1.4.3: 1](#). Dose reductions will apply to individual patients only. Once the treatment dose has been reduced, it cannot be increased later.

To prevent the development of more severe adverse events, treatment related diarrhoea, nausea and vomiting or rash should be managed early and proactively as described in [Section 4.2](#).

Proprietary confidential information.

© 2017 Boehringer Ingelheim International GmbH or one or more of its affiliated companies. All rights reserved.

This document may not - in full or in part - be passed on, reproduced, published or otherwise used without prior written permission.

Table 4.1.4.3:1 Dose reduction scheme for afatinib

AE type and CTCAE Grade	Action	Dose reduction scheme

Events related to study drug:
 
 • Diarrhoea Grade 2 persisting for 7 or more consecutive days despite adequate anti-diarrhoeal medication/hydration • Reduced renal function to \geq Grade 2 as measured by serum creatinine, proteinuria or decrease in glomerular filtration rate of more than 50% from baseline • Any drug related AE Grade \geq3 	
Pause treatment until patient has recovered to Grade \leq1 or baseline¹.
 
Resume treatment at reduced dose according to schedule opposite.
 
If patient has not recovered to Grade \leq1 or baseline¹ within 14 days, study treatment must be permanently discontinued².
	
If patient was treated at dose level 3, resume treatment at dose level 2
 
If patient was treated at dose level 2, resume treatment at dose level 1
 
If patient was treated at dose level 1, resume treatment at dose level 0
 
If patient was treated at dose level 0, resume treatment at dose level -1
 
If patient was treated at dose level -1, discontinue afatinib.

Acute onset and/or unexplained worsening of pulmonary symptoms (dyspnoea requiring supplementation of oxygen with cough and/or fever)
	
Pause afatinib while clinical assessment to exclude ILD is completed.
	
If ILD is ruled out as a cause of symptoms, grade symptoms and relatedness and report as AEs. If AEs are not related, resume afatinib at current dose.
 
If ILD is confirmed, discontinue afatinib.

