© 2017 Boehringer Ingelheim International GmbH or one or more of its affiliated companies. All rights reserved.

This document may not - in full or in part - be passed on, reproduced, published or otherwise used without prior written permission.

wound healing. If afatinib is interrupted for more than 14 days, the decision to continue will be made by the BI Clinical Monitor in agreement with the investigator.

Emergency procedures

Careful assessment of all patients with an acute onset and/or unexplained worsening of pulmonary symptoms (dyspnoea, cough, fever and demand for oxygen supplementation) should be performed to exclude interstitial lung disease (ILD). Study drug should be interrupted pending investigation of these symptoms. If interstitial lung disease is diagnosed, study drug must be permanently discontinued and appropriate treatment instituted as necessary.

Patients who present with symptoms of keratitis, such as acute or worsening eye inflammation, lacrimation, light sensitivity, blurred vision, eye pain and/or red eye should be referred promptly to an ophthalmic specialist. If a diagnosis of ulcerative keratitis is confirmed, treatment with afatinib should be interrupted or discontinued. If keratitis is diagnosed, the benefits and risks of continuing treatment with afatinib should be carefully considered. Afatinib should be used with caution in patients with a history of keratitis, ulcerative keratitis or severe dry eye. Contact lens use is a risk factor for keratitis and ulceration.

In case the patient develops acute onset of symptoms indicative of cardiac failure and/or CTCAE Grade ≥ 2 LVEF decrease and/or $\geq 20\%$ decrease of LVEF from baseline, study drug should be interrupted pending investigation of symptoms. The patient should be monitored closely for recovery. If patient has not recovered despite appropriate treatment to Grade ≤ 1 or baseline within 14 days study treatment must be permanently discontinued.

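### Section 3.3.4.1 item 6 makes any diagnosed keratitis a mandatory stop, while Section 4.2.1 and Table 4.1.4.3:1 leave room to continue; a smaller mismatch affects unrecovered cardiac events

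*Protocol*

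**What the plan says.** The removal list in Protocol Section 3.3.4.1 opens with "A patient is to discontinue study medication if". Item 6 under that lead-in reads "The patient is diagnosed with ILD, keratitis or heart failure (including clinically relevant LVEF reduction"), followed by a bare reference to Section 4.2.1.

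The emergency procedures in Section 4.2.1 handle the three conditions as follows:

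- **ILD:** "If interstitial lung disease is diagnosed, study drug must be permanently discontinued".
- **Keratitis:** prompt referral to an eye specialist, then "If a diagnosis of ulcerative keratitis is confirmed, treatment with afatinib should be interrupted or discontinued", and next "If keratitis is diagnosed, the benefits and risks of continuing treatment with afatinib should be carefully considered".
- **Cardiac:** for symptoms suggesting cardiac failure, an LVEF decrease of Grade 2 or more, or a fall of at least 20% from baseline, "study drug should be interrupted pending investigation of symptoms". For a patient who does not recover to Grade 1 or less, or to baseline, the rule ends "within 14 days study treatment must be permanently discontinued".

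Table 4.1.4.3:1 covers the same ground. For ILD it says "If ILD is confirmed, discontinue afatinib". For keratitis it pauses the drug during assessment and discontinues for confirmed ulcerative keratitis, unless the investigator judges that benefit outweighs the risk of worsening, which it names as blindness. For cardiac events it pauses and applies the same 14-day limit. Footnote 2 is attached to that limit: where the investigator sees obvious clinical benefit, sponsor and investigator may agree on further treatment.

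**The concern.** Section 2.3 lists keratitis and left ventricular dysfunction among the toxicities to be detected early, and points to Section 4.2.1 for the precautions. The removal list is where a site looks to learn whether a patient has to come off drug. For keratitis, the list and the section it cites start from the same event and give different instructions: one says stop, the other says consider continuing.

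At stake is whether a child with confirmed keratitis stays on a drug when the protocol itself names loss of sight as the risk. About 30 sites are expected to recruit, and two of them could treat the same case in opposite ways, each with a protocol section in support.

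**Working it through.** No sample size, rate or error probability enters this point, so the check is a comparison of the three places.

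| Condition | 3.3.4.1 item 6 | 4.2.1 | Table 4.1.4.3:1 |
|---|---|---|---|
| ILD | Stop | Stop | Stop |
| Ulcerative keratitis | Stop | Interrupt or stop | Stop unless investigator judges benefit greater than risk |
| Other keratitis | Stop | Weigh benefit and risk of continuing | Pause during assessment; keratitis row names no stop |
| Cardiac | Stop on heart failure, including an undefined degree of LVEF reduction | Interrupt; stop if not recovered in 14 days | As 4.2.1, but footnote 2 allows continuation even then |

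**Step 1, ILD.** All three agree. This is the benchmark for a consistently stated rule.

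**Step 2, keratitis.** The trigger is the same in item 6 and Section 4.2.1: a diagnosis. Item 6 admits no discretion and Section 4.2.1 grants it explicitly. The table stops treatment only for the ulcerative form, again with discretion. Both are softer than item 6.

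**Step 3, cardiac.** The triggers differ. Item 6 needs a diagnosis; Section 4.2.1 and the table react to symptoms or an LVEF threshold while the cause is investigated. Most of the apparent conflict can be read as a sequence. Two things remain. For a patient not recovered within 14 days, Section 4.2.1 makes the stop mandatory and footnote 2 makes it negotiable. Item 6's qualifier on LVEF reduction is not defined, so it cannot be matched to either rule.

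**Step 4, is there a controlling clause?** The protocol states no order of precedence. Section 5.2.2.1 sends drug-related protocol-specified AESIs to Section 4.1.4.3, and DLTs are such AESIs. By Table 4.1.4.1:2 that takes in a related LVEF decrease of Grade 2 or more and related keratitis of Grade 3 or 4. It does not take in keratitis that is Grade 1–2 or unrelated, nor cardiac events outside the DLT definition. For those, nothing says whether item 6 or the softer text applies.

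**Step 5, analysis.** SAP Table 6.2:1, code C3, classes dose handling contrary to protocol after an AE or DLT as an important deviation, and excludes nobody for it. SAP Section 7.4.2 calculates the response rate on all treated patients. Neither depends on which rule a site followed.

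**The case against.** **Item 6 cites Section 4.2.1, so that section governs.** Items 5 to 7 each name a trigger and point to the detail, and item 7 cannot be applied without its reference. Reading item 6 the same way is reasonable. But it would turn a mandatory stop into no stop for keratitis, which the lead-in does not suggest, and Section 4.2.1 would still differ from the table.

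**Suspicion, pause, work-up, diagnosis, stop.** On this reading the cardiac provisions follow the same sequence as ILD and do not conflict with item 6. No text says outright that treatment may resume after heart failure is diagnosed; resumption is only implied by the pause lasting until recovery. This stands. A reader might infer from item 6 a flat contradiction on cardiac events equal to the one on keratitis; the different triggers do not support that. Footnote 2 and the undefined LVEF term are what remain.

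**The table is the working standard.** The AESI clause in Section 5.2.2.1 points there. So does SAP code C3, which cites protocol dose tables (its number 4.1.2.3:1 appears to be a slip for 4.1.4.3:1). This supports choosing the table as the single rule. It also undercuts any inference that C3 could not be coded consistently. It does not amend item 6.

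**Non-ulcerative keratitis is covered.** The table's keratitis row ends at the pause, and a reader might infer that sites have no instruction. Section 4.2.1 supplies one: specialist referral and a benefit-risk decision.

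**The two texts on ulcerative keratitis are close.** Both halt the drug and leave a route back. The difference is one of default: the table discontinues unless justified, while Section 4.2.1 offers interruption as an equal choice. It is small but should not remain.

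**Limited consequence.** The immediate pause and referral are clear, interruptions beyond 14 days need the sponsor's monitor to agree, a DMC reviews benefit and risk, and item 6 errs toward stopping. All true. None of it tells a site whether keratitis requires a stop.

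**Conclusion.** The inconsistency is real and should be corrected. The firm part is keratitis: a mandatory stop in item 6 against explicit discretion in Section 4.2.1 and a narrower, overridable stop in the table. It is clearest for Grade 1–2 or unrelated keratitis, which the AESI clause does not reach. The cardiac part is smaller: footnote 2 against the unconditional 14-day stop in Section 4.2.1, plus an LVEF term in item 6 that is linked to neither.

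The size is qualitative. Section 2.3 describes keratitis as rarely seen with afatinib, the documents give no rate, and none is assumed here. Confidence is high on keratitis and moderate on the cardiac part, which depends on how the triggers are read. A reader might infer that conflicting stopping rules bias the efficacy results; the documents do not support this, because no analysis set or efficacy estimate is affected.

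**What to change.** Make the three places state one rule:

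1. Reword item 6 to: *ILD, or keratitis or cardiac events meeting the discontinuation rules in Table 4.1.4.3:1*. This also removes the undefined LVEF term.
2. Give Section 4.2.1 the table's rule for ulcerative keratitis: discontinue unless the investigator judges that benefit outweighs risk.
3. For cardiac events not recovered within 14 days, either add the footnote 2 exception to Section 4.2.1 or remove it from the table's cardiac row.

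If the sponsor intends the strict rule, leave item 6's stop in place, remove the discretion from Section 4.2.1 and the table, and define the LVEF reduction that counts. A separate table row for non-ulcerative keratitis is optional, since Section 4.2.1 already covers it.

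The cost is a wording amendment to item 6, Section 4.2.1 and, depending on the option chosen, the keratitis or cardiac row of the table. There is no analysis cost.
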